6.2.2 Treatment phase

At the beginning of each visit during treatment phase, Investigator and site personnel should ensure the well-being of the patient as well as prepare all requirements for conduct of the visits that are necessary.

The order of the different trial procedures should follow the protocol and should be planned for taking into account the specific structure of the investigational site and following the mandatory needs outlined in the clinical trial protocol.

Mandatory needs: the following has to be ensured during trial visits according to the study Flowchart:

- Patient reported outcome questionnaires have to be filled out always prior to any other procedures by the patient in a quiet area and in the following order:
 1. K-BILD
 2. L-PF Symptoms and Impact Questionnaire
 3. EQ-5D
 4. PF-IQOLS
- Urine pregnancy test and any laboratory sample collection must be performed prior trial medication administration.
- FVC and DLCO measurement at all visits should be performed approximately at the same time of the day to reference time point at Visit 2.
- Order of pulmonary function tests must always be
 1. FlowScreen® spirometry (FVC) followed by patient's rest
 2. DLCO with site's own equipment.

Baseline Visit 2 (randomization)

The following prerequisites must be available for randomization:

- Eligibility confirmation and HRCT pattern from central HRCT review.
- Safety laboratory results including haemoglobin and creatinine from Visit 1.

Procedures:

- All patients will be asked to fill out the patient reported outcome questionnaires prior to any other visit procedure. The order of the questionnaires will always be: 1. K-BILD, 2. L-PF Symptoms and Impact Questionnaire, 4. EQ-5D, 5. PF-IQOLS.
- Site personnel will review questionnaires for completeness.
- Physical examination including vital signs and HCRU interview will be performed.
- Adverse events and concomitant therapy since last visit will be reviewed and recorded.
- Medical history will be reviewed.
- Repeated resting 12-lead electrocardiogram using site's own equipment will be performed and evaluated if resting ECG was abnormal at Visit 1 (if possible prior to blood draw).
- SpO₂ will be recorded (earlobe or forehead, resting).
- FVC measurement will be conducted with the FlowScreen® spirometer.
- DLCO measurement with sites own equipment will be conducted.
- All in/exclusion criteria will be assessed based on Visit 1 laboratory and Visit 2 measures.
- HRCT will be performed in patients who agree to have follow-up HRCT done as part of the trial, unless a screening HRCT was done as part of the study to determine eligibility.

- Safety blood and urine samples will be collected and submitted to the central laboratory.
- Biomarker samples will be collected and submitted to the central laboratory.
- The time of blood collection for biomarker samples will be recorded in the eCRF.
Note: blood samples should always be collected prior to drug administration.
- One blood sample for DNA banking will be collected in eligible patients and only after obtaining a separate informed consent.
- Local urine dipstick pregnancy test (if applicable).
- If a patient is eligible for the trial, randomization will be performed by using the IRT system.
- Treatment will be dispensed.
- The next visit will be scheduled and prepared.

Visit 7, Visit 9 and EOT_A ('big visits') procedures

At Visit 7, Visit 9 and EOT_A (primary endpoint visit), the same procedures will be performed as done at baseline Visit 2. Exceptions are the typical randomization measures, e.g. eligibility review, medical history assessment and randomization as well as DNA banking sample which is only taken once. In addition, if EOT takes place before Visit 7, HRCT should not be repeated. For Visit 7, Visit 9 and EOT_A always refer to the [Flowchart Part A](#).

General rules

- Treatment compliance will be reviewed by site personal.
- Trial medication will be collected and/or dispensed according to Flowcharts Part A.
- Visit 9 and end of treatment visit (EOT_A) are identical visits. EOT_A is to be used in eCRF at any time a patient ends trial medication (scheduled or prematurely).
- Patient who prematurely discontinued trial medication will attend all originally planned visits until the end of the trial (except for the laboratory visits 6a, 7a and 8a).
- IRT should always be notified on end of treatment (EOT).
- Vital status will be collected for patients who prematurely discontinued trial medication and failed to attend future visits as planned, as well as for those who did not attend scheduled visits as planned at week 52 (scheduled Visit 9/EOT_A).
- PROs will always be scheduled prior to any other procedure and in the above described order and will be reviewed for completeness by site personal.
- Drug intake at visit days should always be performed at site and after blood and urine sample collection and pregnancy test.
- FlowScreen® spirometry (FVC) and DLCO measurements will always be in the allowed time window and the described order (reference visit = Visit 2).
- Non-elective hospitalization will be recorded.
- Acute ILD exacerbations will be recorded.
- Resting 12-lead electrocardiogram using site's own equipment will be performed and evaluated (if possible prior to blood draw).
- At Visit 7, a PK sample will be collected. The patient needs to record exact date and clock time of medication intake the preceding three days on a PK-card provided at

Visit 6. The date and time of blood collection for PK and drug administration at the site will be recorded.

- Biomarker blood sampling will be done. The date and time of blood collection for biomarker samples will be recorded in the eCRF.
- For patients who agreed to the optional HRCT-follow-up, HRCT should be done at V7 and V9.

Visit 3, 4, 5, 6, and 8 ('medium visits') procedures

Please note that not all medium visits are drug dispensation visits (please always refer to [Flowchart Part A](#)). However, compliance of patients regarding drug intake should always be reviewed (see also treatment compliance in [Section 4.3](#)).

- Physical examination including vital signs and HCRU interview will be performed.
- Adverse events and concomitant therapy since last visit will be reviewed and recorded.
- PROs will be scheduled prior to any other procedure and in the above described order and will be reviewed for completeness by site personal at Visits 6 and 8.
- Local dipstick pregnancy test (if applicable).
- Safety blood and urine samples will be collected and submitted to the central laboratory.
- At medium Visits 6 and 8, biomarker samples will be collected. The date and time of blood collection for biomarker samples will be recorded in the eCRF.
- At medium Visit 4, a PK sample will be collected. The patient needs to record exact date and clock time of medication intake the preceding three days on a PK-card provided at Visit 3. The date and time of blood collection and drug administration at the site will be recorded.
- At medium Visit 6, a PK-card will be provided to record exact date and clock time of medication intake three days preceding PK sampling at Visit 7.
- FlowScreen® spirometry (FVC) in the allowed time window will be performed.
- Non-elective hospitalization will be recorded.
- Acute ILD exacerbations will be recorded.
- 2 to 3 take home pregnancy tests (dipsticks) at Visit 8 will be dispensed.
- Treatment compliance will be reviewed by site personal at every visit (except at randomization visit and at 'a-Visits').
- Trial medication will be collected and/or dispensed according to Flowchart Part A.

Visit X and EOT_B procedures

- Physical examination including vital signs and HCRU interview will be performed.
- Adverse events and concomitant therapy since last visit will be reviewed and recorded.
- Local dipstick pregnancy test (if applicable).
- Safety blood and urine samples will be collected and submitted to the central laboratory.

Proprietary confidential information © 2018 Boehringer Ingelheim International GmbH or one or more of its affiliated companies

- Resting 12-lead electrocardiogram using site's own equipment will be performed and evaluated (if possible prior to blood draw) at every other visit and EOT.
- The date and time of blood collection and drug administration at the site will be recorded.
- FlowScreen® spirometry (FVC) and DLCO measurements in the allowed time window will be performed.
- Non-elective hospitalization will be recorded.
- Acute ILD exacerbations will be recorded.
- Home pregnancy tests (dipsticks) will be dispensed.
- Treatment compliance will be reviewed by site personal at every visit.
- Trial medication will be collected and/or dispensed according to [Flowchart Part B](#).
- Assessment of vital status at EOT_B visit

Intermediate 'a-Visit' procedures

- Safety blood, pregnancy tests and urine samples will be collected and submitted to the central laboratory if needed for additional safety monitoring at the discretion of the Investigator (see [Section 4.2.2.2](#)).

6.2.3 Follow-up Visit and trial completion

A Follow-up Visit has to be scheduled 28 days after End of Treatment Visit for all patients except for patients transferred into a separate open-label extension study. This Follow-up Visit is the safety follow-up after treatment discontinuation.

- Physical examination including vital signs.
- Adverse events and concomitant therapy will be assessment since last visit.
- Local dipstick pregnancy test (if applicable).
- FlowScreen® spirometry (FVC) in the allowed time window will be performed.
- Non-elective hospitalization will be recorded.
- Acute ILD exacerbations will be recorded.
- Patient's participation will be concluded for patients who withdraw consent and do not attend future visits.

Trial completion

The trial completion eCRF page has to be filled-in when the patient has terminated the trial. The end of the trial for the individual patient is:

- For patients who complete all study visits, end of trial is EOT_B. A follow-up visit is only required for those who do not roll-over in the separate open-label study
- For patients who withdraw consent
 - at time of trial medication discontinuation, end of trial is an EOT visit followed by a follow-up visit.

- after EOT was already completed, then the patient should have a final visit based on their scheduled study visit.

Patients who prematurely discontinued trial medication

In case a patient has to permanently discontinue trial medication, for whatever reason, he/she will be encouraged to attend all future visits up to end of trial as originally planned (except for the laboratory ‘a-Visits’).

- During these visits, the patient will undergo all planned examinations according to [Flowcharts A](#) and [B](#), especially FlowScreen® spirometry (FVC) and will fill in the PRO questionnaires (only Part A); however he/she will not have to do the resting ECG, safety laboratory, biomarker laboratory and PK blood draw.
- These visits will be regarded as part of the trial despite the patient having discontinued trial medication.

The need for coming to future visits in case of prematurely discontinuation of trial medication will be explained to patients prior to their participation in the trial.

Vital status information

In case of premature discontinuation of trial medication, if the patient does not attend future visits as planned, every attempt will be made to get information on vital status at 52 weeks after his/her randomization, at the time of data cut-off for the primary analysis and at the end of the trial for patients who have withdrawn consent.

Patients will be asked to agree to be contacted by the site personnel, which could be by telephone calls, to allow collection of the vital status.

If death occurs, the Investigator will review the circumstances, including the relevant medical records to ascertain the most likely primary and secondary causes of death. The cause of death will be adjudicated by the AC.

Collection of vital status will be performed in accordance with national ethical and regulatory guidelines.

6.2.4 Dose reduction visit / dose increase visit

If a patient experiences a drug related adverse event, the dose can be reduced and the dose can be re-increased after recovery as described in [Section 4.2.1](#). In both cases, the patient will have to come back to a visit where the following will be performed:

- Physical examination including vital signs.
- Adverse events and concomitant therapy will be assessment since last visit.
- Local dipstick pregnancy test (if applicable).

- Safety blood and urine samples will be collected and submitted to the central laboratory.
- FlowScreen® spirometry (FVC) in the allowed time window will be performed.
- Trial medication will be collected and treatment compliance will be reviewed.
- IRT call for reduction or increase of the dose and trial medication dispensation.

7. STATISTICAL METHODS AND DETERMINATION OF SAMPLE SIZE

7.1 STATISTICAL DESIGN - MODEL

This is a multi-centre, multi-national, prospective, randomized, placebo-controlled, double blind trial to investigate the efficacy and safety of nintedanib 150 mg bid over 52 weeks in patients with PF-ILD.

The primary endpoint is the annual rate of decline in FVC estimated from readings taken over 52 weeks. The annual rate of decline in FVC will be analysed using a random coefficient regression (random slopes and intercepts) model including baseline FVC in mL and HRCT pattern (except for the analyses on the co-primary population assessing only patients with HRCT with UIP-like fibrotic pattern only) as covariates.

7.2 NULL AND ALTERNATIVE HYPOTHESES

The superiority of nintedanib 150 mg bid compared to placebo will be tested for the annual rate of decline in FVC in mL.

For the overall population, the null hypothesis is:

H_0 : There is no difference in the annual rate of decline in FVC in mL between nintedanib 150 mg bid and placebo in the overall population.

The alternative hypothesis is:

H_a : There is a difference in the annual rate of decline in FVC in mL between nintedanib 150 mg bid and placebo in the overall population.

For the co-primary population of patients with HRCT with UIP-like fibrotic pattern only, the null hypothesis is:

H_0 : There is no difference in the annual rate of decline in FVC in mL between nintedanib 150 mg bid and placebo in the patients with HRCT with UIP-like fibrotic pattern only.

The alternative hypothesis is:

H_a : There is a difference in the annual rate of decline in FVC in mL between nintedanib 150 mg bid and placebo in patients with HRCT with UIP-like fibrotic pattern only.

In order to maintain an overall type 1 error rate of 5%, a Hochberg procedure will be used ([R97-1003](#)). For the primary endpoint, statistical significance will be declared if the analyses in both co-primary populations are significant at the two-sided 5% level, or if the analyses in either co-primary population are statistically significant at the two-sided 2.5% level.

[figure not shown]

Figure 7.2: 1

Scenarios for statistical significance using Hochberg procedure

7.3 PLANNED ANALYSES

The efficacy and safety analyses will be conducted on the treated set (TS), which consists of patients who are randomized to a treatment group and receive at least one dose of study medication. There will be two co-primary analysis populations: the first will comprise all patients from the treated set (the overall population); the second will comprise all patients from the treated set with HRCT with UIP-like fibrotic pattern only.

The primary assessment of benefit-risk of nintedanib in patients with PF-ILD will be based on efficacy and safety data over 52 weeks (including data from part A only); assessments performed within the first 52 weeks (time-windowing rules will be defined in the TSAP) will be used.

The primary analysis is a random coefficient regression (random slopes and intercepts) model including baseline FVC (mL) and HRCT pattern (except for the analyses on the co-primary analysis population assessing only patients with HRCT with UIP-like fibrotic pattern only) as covariates.

Efficacy and safety data over the whole trial (including data from part A and part B) will be reported descriptively only. Data collected in Part B of the trial and available at the time of the primary analysis data cut-off will be reported after the first database lock. Selected analyses will be repeated after the final database lock and will include data collected until the end of the trial.

All analyses will be based on the treatment group (nintedanib 150 mg bid or placebo) as randomized by IRT.

Although there is no per protocol data set in the study, reasons for important protocol violations will be specified in the Trial Statistical Analysis Plan (TSAP). Patients with important protocol violations will be identified at Blinded Review Planning Meetings and listed in the CTR.

7.3.1 Primary endpoint analyses

The primary endpoint is defined in [Section 5.1.1](#).

Baseline FVC in mL will be included as a covariate in the analysis model. Baseline FVC is defined as the FVC result recorded at Visit 2, unless missing in which case the screening result will be used. The HRCT pattern (“UIP-like fibrotic pattern only” or “Other fibrotic patterns”) will also be used as a covariate for the analysis performed on the overall population and will not be a covariate for the analysis on the co-primary population assessing only patients with HRCT with UIP-like fibrotic pattern only. The primary analysis will also be performed on the complementary population of patients with other HRCT fibrotic patterns. A forest plot will present the three placebo-corrected, adjusted annual rates of decline in FVC with 95% confidence intervals from the analyses on the co-primary populations and on the complementary subgroup population.

The decrease in FVC is assumed to be linear within each subject over 52 weeks; this was also assumed in the IPF trials INPULSIS-1 and INPULSIS-2 ([P14-07514](#)). The intercepts and slopes will be assumed to be normally distributed with arbitrary covariance matrix. The within patient error will be assumed to be independent and normally distributed with mean zero and a common variance. The Kenward-Roger approximation will be used to estimate denominators degrees of freedom. Significant tests will be based on least-squares means; p-values and two-sided 95% confidence intervals for the difference between the treatment groups will be presented. An intent-to-treat principle will be used (i.e. all available data from the treated set within the first 52 weeks will be used, including baseline and data retrieved post treatment discontinuation for patients who prematurely discontinued randomized treatment). Analyses will be implemented using SAS® Version 9.4 or higher.

The assumptions for the primary analysis of decline in FVC will be tested; details will be provided in the TSAP. The primary analysis will be based on observed data (but including retrieved drop out measurements) and will assume remaining missing data are missing at random. The effect of missing data will be investigated using multiple imputation methods which assume that patients who discontinue treatment will no longer benefit from it in the future. See [Section 7.5.1](#) for further details of these sensitivity analyses.

Subgroup analyses will be specified in the TSAP and will include:

- Age
- Gender
- Original diagnosis (e.g. IIP; CTD-ILD; other ILDs)

A cumulative distribution plot will be provided, showing the percentage of patients by the change from baseline in FVC in mL at Week 52.

Data will be summarized graphically and using summary statistics.

7.3.2 Secondary endpoint analyses

Secondary endpoints are defined in [Section 5.1.2](#).

For all secondary endpoints, an intent-to-treat principle will be used (i.e. all available data from the treated set within the first 52 weeks will be used, including data for patients who prematurely discontinued randomized treatment).

Continuous endpoints will be analysed using a restricted maximum likelihood (REML) based repeated measures approach. Analyses will include the fixed, categorical effects of HRCT pattern (except for the analyses on the co-primary analysis population assessing only patients with HRCT with UIP-like fibrotic pattern only), treatment, visit, and treatment-by-visit interaction, as well as the continuous, fixed covariates of baseline and baseline-by-visit interaction. An unstructured (co)variance structure will be used to model the within-patient measurements.

If this analysis fails to converge, the following covariance structures will be tested in order: heterogeneous toeplitz (TOEPH), toeplitz (TOEP) and autoregressive 1 (AR[1]). The first model to converge will be used. The Kenward-Roger approximation will be used to estimate denominator degrees of freedom. Significance tests will be based on least-squares means using a two-sided $\alpha = 0.05$ (two-sided 95% confidence intervals). In case the model fails to converge under PROC MIXED, the “singular” option will be considered. The treatment comparisons will be the contrast between treatments at week 52.

Time-to-event endpoints will be analysed using a Cox proportional hazards model. The equality of the hazard rates will be tested by the Wald test for the treatment effect at the two-sided 5% significance level. The model will include the treatment effect and HRCT pattern (except for the analyses on the co-primary analysis population assessing only patients with HRCT with UIP-like fibrotic pattern only) as covariates. Breslow’s method for handling ties will be used. Kaplan-Meier plots by treatment group will also be presented. If the proportion of patients experiencing at least 1 acute ILD exacerbation over 52 weeks is less than 2%, then only frequencies of exacerbations by treatment group will be provided for the main secondary endpoint of time to first acute ILD exacerbation or death over 52 weeks and no statistical analysis will be performed.

Comparisons between treatment groups regarding the binary endpoint variables based on categorical declines in FVC % predicted (% pred) will be performed using a logistic regression model adjusting for the continuous covariate baseline FVC % pred and the binary covariate HRCT pattern (except for the analyses on the co-primary analysis population assessing only patients with HRCT with UIP-like fibrotic pattern only). The likelihood-ratio test will be used to test for differences between treatments. Adjusted odds ratios together with 95% confidence intervals will be used to quantify the effect of treatment, comparing nintedanib 150 mg bid to placebo as the reference.

Any p-values presented for the secondary endpoints will be considered nominal in nature and no adjustment for multiplicity will be made.

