5.2.2.2.2 Time to progression or death over 52 weeks

Progression is defined as the date when $\geq 10\%$ of absolute decline in FVC % pred compared to baseline occurs for the first time.

For those patients who fulfil the criteria for progression or death due to any cause within the first 52 weeks, time to progression or death due to any cause [days] will be computed as:

- Earliest of date of documented progression event or death – date of first drug intake + 1

Patients who did not experience any event within the first 52 weeks will be censored according to the mechanism for censoring as described in [Table 5.2.2.2.2: 1](#).

Table 5.2.2.2.2: 1 Censoring Rules for Time to progression or death over 52 weeks

Rule #	Situation	Outcome (event or censored)	Date of event or censoring
1	Patient had a documented progression or died within the first 52 weeks and the date of the event is known	Event	Earliest Date of event
2	Patient had a documented progression or died within the first 52 weeks and the date of the event is unknown	Event	Imputed date of event
3	Patient did not have a documented progression and is alive after 52 weeks	Censored	Day 373 (372 days after first drug intake)
4	Patient status is unknown	Censored	Date of last contact when the patient was known to be alive and event free

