7.5.2.1.2 Time to death

A stratified log-rank test will be used to evaluate the effect of Nintedanib on time to death compared to Placebo. The test will be stratified by the randomisation stratification variable HRCT pattern ("HRCT with UIP-like fibrotic pattern only" vs. "Other HRCT fibrotic patterns", as documented in the CRF). A Cox proportional-hazards model stratified by the same factors as the log-rank test will be used to derive the hazard ratio and 95 % confidence interval (CI) between the two randomised treatment regimens (Hazard ratios <1 will favour nintedanib). In the co-primary population of patients with "HRCT with UIP-like fibrotic pattern only", the respective analyses will be performed without stratification.

Breslow's method for handling ties will be used. Kaplan-Meier plots by treatment group will also be presented. The assumption of proportional hazards and the homogeneity of the hazard ratio will be checked descriptively.

If the proportion of patients experiencing an event is less than 5%, only frequencies of events by treatment group will be provided for this endpoint. In this case no other analyses will be performed.

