7.5.2.2.2 Time to progression or death

The same type of evaluation as described for time to death (see [Section 7.5.2.1.2](#)) will be implemented for this endpoint. If, however, the proportion of patients experiencing a progression (see [Section 5.2.2.2.2](#) for details about the definition of progression) within the 52 week period is less than 5%, then only frequencies of events by treatment group will be provided. In this case no other analyses will be performed.

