7.5.2.2.3 Relative decline from baseline in FVC % pred

Patients will be categorised based on the relative decline since baseline in FVC % pred greater than 5% or 10%. Comparisons between treatment groups will be performed using a logistic regression model adjusting for the continuous covariate baseline FVC % pred and the binary covariate HRCT pattern. The likelihood-ratio test will be used to test for differences between treatments. Adjusted odds ratios together with 95% confidence intervals will be used to quantify the effect of treatment, comparing nintedanib 150 mg bid to placebo as the reference. Additionally, descriptive analyses of the relative change from baseline in FVC % pred will be shown, for the co-primary populations as well as for the complementary population.

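### Time to a 10-point FVC % predicted decline or death is the one modelled FVC endpoint not adjusted for baseline; adding baseline is a small, cheap improvement to its hazard ratio

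*Protocol*

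**What the plan says.** **Time-to-event model.** Protocol 7.3.2 gives all time-to-event endpoints one Cox model: "The model will include the treatment effect and HRCT pattern". SAP 4.2 replaces the Wald test with a stratified log-rank test, and SAP 7.5.2.1.2 sets out the estimate: "A Cox proportional-hazards model stratified by the same factors as the log-rank test will be used to derive the hazard ratio". In the UIP-like population both are unstratified. For time to progression or death, SAP 7.5.2.2.2 prescribes "The same type of evaluation as described for time to death", and SAP 7.6.2.4 carries that over to the whole trial.

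**The event.** SAP 5.2.2.2.2 dates progression to when a ≥10% "absolute decline in FVC % pred compared to baseline occurs for the first time".

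**The other FVC models.** Protocol 7.3.2 analyses the categorical declines with a "logistic regression model adjusting for the continuous covariate baseline FVC % pred". SAP 7.5.2.2.3 keeps this, "adjusting for the continuous covariate baseline FVC % pred and the binary covariate HRCT pattern", and SAP 7.6.1.3 uses the same model for the absolute declines of more than 5% and more than 10% at week 52. The primary model (SAP 7.4.1) has baseline FVC and its interaction with time. The repeated-measures models for FVC change (SAP 7.6.1.2) have baseline and its interaction with visit.

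**Availability of baseline.** FVC % predicted at Visit 2 is an entry criterion (Protocol 3.3.2), and a screening value stands in if the Visit 2 FVC is missing (Protocol 7.3.1).

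Neither document says why progression is treated differently.

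**The concern.** The event is a change from baseline, so the baseline value and its measurement error are part of the event's definition. A fixed 10-point fall is also a different relative loss at different starting points: 10/90 = 11% at a baseline of 90, and 10/45 = 22% at the entry limit of 45. Baseline FVC % predicted could therefore plausibly predict when the event occurs.

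If it does, leaving it out of the Cox model has three effects. The hazard ratio moves towards 1, because it averages over patients of differing risk. It shifts with whatever baseline difference chance produces between the arms. And it is not conditioned in the same way as the odds ratios for decline at week 52, although both address FVC % predicted decline.

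The hazard ratio and its interval are what this endpoint will be read by. SAP 4.3 and 7 show p-values, among secondary endpoints, only for the main ones, and progression or death is an other secondary endpoint.

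**Working it through.** **1. The plan's own figures.** The documents give no power or event count for progression or death. The power they do state concerns the primary endpoint. Recoding the Protocol 10.6 macro gives an alpha of 4.348% (stated 4.35%) and Scenario 1 overall power of 92.55% (stated 92.6%). These have no bearing on the choice of covariate here.

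**2. Closest comparison.**
- Absolute decline >10% at week 52 (SAP 5.3.1.3, 7.6.1.3): same measurement, same baseline; adjusted for baseline FVC % predicted and HRCT pattern.
- Time to absolute decline ≥10% or death (SAP 5.2.2.2.2, 7.5.2.2.2): HRCT stratification only.

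**3. Likely number of events.** Protocol 1.2 gives a pooled IPF hazard ratio of 0.60 (95% CI 0.49 to 0.74) for the same type of event, with 2:3 allocation. Protocol 10.5 gives placebo groups of 204 and 219.
- SE(log HR) = (ln 0.74 − ln 0.49)/3.92 = 0.105
- Events = 1/(0.4 × 0.6 × 0.105²), about 377 with the unrounded SE
- Patients = (204 + 219) × 2.5, about 1,058; event proportion 35.6%; about 214 events in 600
- At 210 events, 1:1: SE = 2/√210 = 0.138; Schoenfeld power is 95.9% at HR 0.60 and 73.4% at HR 0.70

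**4. Cox model without and with the covariate.** Simulation with 600 patients, 1:1, 2:1 HRCT strata, 52-week censoring, an assumed 40% placebo risk and 1,500 trials per row. The prognostic strength of baseline is not in the documents, so it is varied. Power is that of a Wald test on the log HR, used only as a yardstick. True HR 0.60:

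| Baseline HR per SD | HR, without → with | SE, without → with | Power, without → with |
|---|---|---|---|
| 1.00 | 0.600 → 0.600 | 0.1453 → 0.1455 | 94.2% → 94.3% |
| 1.49 | 0.610 → 0.600 | 0.1449 → 0.1452 | 93.5% → 95.0% |
| 2.01 | 0.635 → 0.605 | 0.1436 → 0.1441 | 88.7% → 93.7% |
| 2.72 | 0.658 → 0.601 | 0.1419 → 0.1429 | 84.7% → 94.9% |

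At a true HR of 0.70 the gain runs from 0 to 15 points over the same range. At a true HR of 1.0, rejection is 4.5–5.5% with or without the covariate. The standard error never falls; what changes is the estimate.

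**5. How prognostic might baseline be?** Simulated FVC % predicted trajectories, deaths included, with assumed baseline mean 70, SD 15 and visit error 3 points (800 trials per setting). The baseline HR per SD was 0.99–1.64, the power gain 0 to 1.8 points, and the SE change at most +0.0003. In the most prognostic setting the HR went from 0.673 to 0.664. The bottom two rows of the table are therefore beyond what these trajectories produce.

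**6. Chance imbalance.** Two further sets of simulations used the same baseline mean and SD, visit error of 2.5–3.5 points and decline halved on drug.
- 1,500 trials per setting: hazard ratio per 10 points of baseline 1.06–1.31; in 1 trial in 20 the unadjusted HR shifts by 2–7% relative to the adjusted one; adjustment worth 0–4% of the sample size.
- 400 trials per setting: 1.06–1.27, 2–6% and 0–5% respectively. The shift correlated 0.74–0.91 with the arms' baseline difference.

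These describe the FVC event; the 400-trial runs had no deaths and no HRCT strata.

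**The case against.** The plan is uniform by endpoint type: every time-to-event endpoint gets the same HRCT-stratified analysis, and the Cox model matches the log-rank test. Allocation is randomised in about 600 patients, so the unadjusted interval already allows for chance imbalance. With an SE of 0.138 that interval spans a factor of exp(1.96 × 0.138) = 1.31 each way, which dwarfs a 2–7% shift seen in 1 trial in 20. Baseline FVC % predicted is tabulated by arm (SAP 5.4.1.3, 7.1), so an imbalance would be visible. The secondary categorical endpoints are relative declines; the absolute declines, the closest comparison, are only exploratory further endpoints. Deaths complicate the direction: a high baseline makes a 10-point fall easier to reach, while a low one plausibly raises the risk of death, and the two may offset.

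All of this stands, and it keeps the point small. It does not explain why the same measurement is adjusted in one model and not in the other, and uniformity by endpoint type is not offered in the documents as the reason.

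A reader might infer more: that the unadjusted hazard ratio carries avoidable noise, or that precision is being thrown away. That does not follow. In a Cox model, omitting a prognostic covariate does not inflate the standard error of the treatment effect; in the table above, adjustment leaves it equal or slightly larger. Nor is there a bias or a type I error problem. The unadjusted hazard ratio is a valid but less conditional quantity.

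**Conclusion.** The inconsistency is confirmed in the protocol and remains in the SAP, without a stated reason. Its consequence is a hazard ratio that, if baseline is prognostic, is mildly attenuated towards 1, moves with chance baseline imbalance, and is conditioned differently from the odds ratios.

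The gain from adjusting is about 0–5% of the sample size, or 0–2 points of power. This rests on assumed baseline mean, SD, measurement error and decline pattern, none of which the documents give. It would be larger only if the baseline hazard ratio per SD were about 2 or more, for which the documents offer no support. The endpoint is an other secondary one, outside the Hochberg procedure, and its whole-trial version is exploratory. This is a worthwhile refinement and no threat to the trial's conclusions.

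**What to change.** In SAP 7.5.2.2.2, and likewise in 7.6.2.4, state that the Cox model giving the hazard ratio and 95% confidence interval for time to progression or death also includes continuous baseline FVC % predicted. Keep it stratified by HRCT pattern in the overall population and unstratified in the UIP-like population. Leave the log-rank test unchanged. Record the difference from Protocol 7.3.2 in SAP 4.2, before the first database lock and unblinding.

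The cost is one covariate in wording and code, using a value required at entry. The downside is that the hazard ratio becomes conditional on baseline FVC % predicted and no longer corresponds exactly to the log-rank test. Showing the HRCT-only hazard ratio alongside deals with that. If the sponsor prefers the present model, one sentence giving the reason would be enough.
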